7. ADVERSE EVENTS: LIST AND REPORTING REQUIREMENTS

Adverse event (AE) monitoring and reporting is a routine part of every clinical trial. The following list of AEs (Section 7.1) and the characteristics of an observed AE (Section 7.2) will determine whether the event requires expedited reporting (via Mandatory Medwatch Forms 3500a) **in addition** to routine reporting in OnCore.

7.1 Adverse Event List(s) for Concentrated Beet Root

BEET ELITE™ is an oral concentrated beet root dietary supplement and not specifically FDA approved. Since BEET ELITE™ is not a drug, there is no Investigator Brochure. This supplement will be obtained from Neogenis® Labs, Inc., Austin, Texas. The BEET ELITE™ product is made from organic beet root crystals, natural flavors, malic acid, and stevia extract and is manufactured in a GMP certified facility. The concentration of the shot is equivalent to 6 beets in one shot.

Beet Root Toxicities:

Potential adverse effects of beet root are rare and include: stomach cramping/diarrhea, pink coloration of urine and stools, and allergic reactions. These side effects are consistent with events that may occur with normal beet consumption (as a food). There have been no reports of mucosal injury in the head and neck, or irritating effect on the oral mucosa.

Methemoglobinemia has been reported in infants who have consumed high levels of nitrate, but these findings have largely been discredited due to confounding cases of gastroenteritis and co-ingestion of sodium nitrite (from contaminated well water). Methemoglobinemia has not been documented in adults consuming nitrates at the level proposed in this trial. Given the oxalate content of beet root (28), caution should be taken for individuals with a history of nephrolithiasis or gall bladder dysfunction.

7.2 Adverse Event Characteristics

- **CTCAE term (AE description) and grade:** The descriptions and grading scales found in the revised NCI Common Terminology Criteria for Adverse Events (CTCAE) version 4.0 will be utilized for AE reporting. All appropriate treatment areas should have access to a copy of the CTCAE version 4.0. A copy of the CTCAE version 4.0 can be downloaded from the CTEP web site: http://ctep.cancer.gov/protocolDevelopment/electronic_applications/ctc.htm.
- **For expedited reporting purposes only:**
 - AEs for the agent(s) that are listed above should be reported only if the adverse event varies in nature, intensity or frequency from the expected toxicity information which is provided.
 - Other AEs for the protocol that do not require expedited reporting are outlined in the next section (Expedited Adverse Event Reporting) under the sub-heading of Protocol-Specific Expedited Adverse Event Reporting Exclusions.

- **Attribution** of the AE:
 - Definite – The AE *is clearly related* to the study treatment.
 - Probable – The AE *is likely related* to the study treatment.
 - Possible – The AE *may be related* to the study treatment.
 - Unlikely – The AE *is doubtfully related* to the study treatment.
 - Unrelated – The AE *is clearly NOT related* to the study treatment.

7.3 Expedited Adverse Event Reporting

7.3.1 For MCC Investigator-Initiated Trials (IITs), investigators **must** report to the Overall PI any serious adverse event (SAE) that occurs after the initial dose of study treatment, during treatment, or within 30 days of the last dose of treatment on the local institutional SAE form. This applies to the following categories:

- **Grade 3 (severe) Medical Events** – Only events that are Unexpected and Possibly, Probably or Definitely Related / Associated with the Intervention.
- **ALL Grade 4 (life threatening or disabling) Medical Events** – Unless expected AND specifically listed in protocol as not requiring reporting.
- **ALL Grade 5 (fatal) Events** regardless of study phase or attribution

Note: If subject is in Long Term Follow Up, death is reported at continuing review.

Note: Abnormal laboratory values are not considered medical events, unless determined to be causative of SAE by the investigator or grade 5

7.3.2 The following table outlines the required forms and reporting structure for clinical trials.

Study type	Expedited reporting to MCC	Expedited reporting to External Agency	Non-expedited AE	Form	IRB
IIT where MCC investigator holds the IDE or IND	
 Grade 3 – Unexpected AE PLUS Possibly, Probably or Definitely Related ALL Grade 4 Unless expected AND listed in protocol as not requiring reporting. ALL Grade 5 (fatal) Events 	FDA: Suspected AE that is serious and Unanticipated (not listed in consent)	OnCore and DSMC reporting only	Mandatory Medwatch 3500a for Serious and unanticipated OnCore for all AEs, including SAEs	Yes if it meets the IRB reporting requirements: Unanticipated Problem and/or Serious AE (use IRB AE reporting form for all correspondence with IRB)

7.3.3 MCC Expedited Reporting Guidelines for MCC IITs

Investigators within MCC will report SAEs directly to the MCC DSMC per the MCC DSMC SOP and the University of Kentucky IRB reporting policy.

Attribution	MCC Reportable AEs				
	Gr. 2 & 3 AE Expected	Gr. 2 & 3 AE Unexpected	Gr. 4 AE Expected	Gr. 4 AE Unexpected	Gr. 5 AE Expected or Unexpected
Unrelated Unlikely	Not required	Not required	5 calendar days [#]	5 calendar days	24 hours*
Possible Probable Definite	Not required	5 calendar days	5 calendar days [#]	5 calendar days	24 hours*
# If listed in protocol as expected and not requiring expedited reporting, event does not need to be reported.					
* For participants enrolled and actively participating in the study or for AEs occurring within 30 days of the last intervention, the AE should be reported within 24 business hours of learning of the event.					

7.3.4 Protocol-Specific Expedited Adverse Event Reporting Exclusions

N/A

7.4 Expedited Reporting to External Agencies

The Overall PI will comply with the policies of all external funding agencies and the UK IRB regarding expedited reporting, as per the UK IRB's SOP:
http://www.research.uky.edu/ori/SOPs_Policies/C4-0150-Mandated_Reportng_to_External_Agencies_SOP.pdf.

7.4.1 Expedited Reporting to the Food and Drug Administration (FDA)

The Overall PI, as study sponsor, will be responsible for all communications with the FDA. The Overall PI will report to the FDA, regardless of the site of occurrence, any serious adverse event that meets the FDA's criteria for expedited reporting following the reporting requirements and timelines set by the FDA.

7.4.2 Expedited Reporting to Hospital Risk Management

Participating investigators will report to the UK Office of Risk Management any participant safety reports or sentinel events that require reporting according to institutional policy.

7.5 Routine Adverse Event Reporting

All Adverse Events **must** be reported in routine study data submissions to the Overall PI on the OnCore case report forms. **AEs reported through expedited processes (e.g., reported to the IRB, FDA, etc.) must also be reported in routine study data submissions.**

8. PHARMACEUTICAL INFORMATION

A list of the adverse events and potential risks associated with the commercial agents administered in this study can be found in Section 7.1.

8.1 Beet Root Juice

8.1.1 List of Supplement Ingredients

- Ingredient List: Organic Beetroot Crystals, Natural Flavors, Malic Acid and Stevia Leaf Extract
- Neogenis® Labs is not able to release proprietary information that describes the specific formulation because of product competitors and privacy issues.

8.1.2 Beet Root Juice (BEET ELITE™) Product Description

Product description: BEET ELITE™ is an oral concentrated beet root dietary supplement. One 10g packet contains both nitrate and nitrite. Typically, only about 5% of beet nitrates are metabolized to active intermediates taking at least 90 minutes. BEET ELITE™ is a revolutionary formula that includes a natural form of nitrite, thus bypassing the inefficient nitrate reduction process. BEET ELITE™ begins working in 15 minutes and has the Nitric Oxide content of 6 beets in one shot. The recommended dose is typically one shot per day. Product is available through Neogenis® Labs, inc., and is available online as a dietary supplement.

8.1.3 Solution preparation:

BEET ELITE™ products are individually packaged in 10g packets and must be mixed with 120ml of water and consumed within 30 minutes of mixing. Participants will be taught to prepare and self-administer their assigned study supplement and IDS will provide participants with the water and powder packet during the IMRT treatment period.

8.1.4 Route of administration:

BEET ELITE™ products will be self-administered throughout the entire study period via enteral

tube (PEG) or by mouth as a thin liquid (PO). Participants will be asked to take this product mixed with water (120ml) daily (M-F) without supervision. Participants will be instructed to administer BEET ELITE™ in the afternoon hours by mouth or by using their PEG tube in accordance with standard PEG feeding tube guidelines. Participants should flush their feeding tube with 30-50mL of water before and after supplementation. This supplement can be served cold or at room temperature within 30 minutes of mixing and may be tolerated best at room temperature if given enterally.

8.2 Labeling:

8.2.1 BEETELITE Labeling

Below is a copy of the container label for a single dose NEoShot product.

Nutrition Facts	
Serving Size: 1 pack (10g)	
Servings Per Container: 10	
Amount Per Serving	% Daily Value*
Calories 30	Calories from Fat 0
Total Fat 0 g	0%
Sodium 15 mg	0%
Potassium 170 mg	2%
Carbohydrates 8 g	1%
Sugars 7 g	
Protein 0 g	
Not a significant source of saturated fat, trans fat, cholesterol, dietary fiber, Vitamin A, Vitamin C, Iron and Magnesium.	
*Percent Daily Values are based on a 2,000 calorie diet.	

8.2.2 **The following label will be used for the study medication**

NAME:

PI: Dr. [name]

PATIENT NO:

DATE:

**Mix with 120mls of water and take by mouth
or via PEG daily as directed. PROTOCOL:13-HN-23-MCC
NEoShot or PLACEBO POWDER 10GM
(Store between 59-86 F) Sponsor:Markey Cancer Center
Caution: New Drug - Limited by Federal Law
to investigational use**

9. BIOMARKER, CORRELATIVE, AND SPECIAL STUDIES

CCTS testing procedures are described below in the planned order of occurrence on testing days:

9.1 Assessment of Body Composition and Quality of Life

9.1.1 Computed Tomography (CT)

Immediately following or preceding radiation simulation (Correlative Day 1) radiation treatment (Correlative Day 2) and follow-up period (Correlative Day 3) at the Markey Cancer Center, subjects will be transported to the ground level of Markey by MCC staff for CT measures.

Computed tomography (CT) images (GE large bore 16 slice) will be used to quantify skeletal muscle and fat area of the right and left thighs, and the right and left forearms of each subject using 100mA with a scanning time of 3 s and a 512 X 512 matrix. With the subject supine, one 10 mm thick cross-section scan of both legs will be taken corresponding to the midpoint between the inguinal crease and the proximal border of the patella, and one 10 mm thick cross-section scan will be taken corresponding to 2/3 the distance from the styloid process of the radius to the olecranon. Tissue area quantification will be determined using corresponding attenuation values of ≥ 200 HU; -190 to -30 HU; and 0-100 HU for bone, adipose tissue, and skeletal muscle, respectively using available software (NIH ImageJ; <http://rsbweb.nih.gov/ij/>). Total thigh fat will be further subdivided into two compartments including the fat above the fascia lata (subcutaneous thigh fat) and below the fascia lata (deep thigh fat). In addition, the skeletal muscle will be subdivided into areas of low attenuation (0-34 HU) representing "fat-rich" muscle, and high attenuation values (35-100 HU) representing muscle with normal fat content. While the forearm scan methodology is unique and has been developed specifically for this study, the method of analyzing thigh composition has been previously described (9). All CT scans will be assessed under the direction of [name].

9.1.2 Quality of Life

Following CT measures at Markey, subjects will be transported to the CCTS for Quality of Life and DXA measures. Quality of life (FACT H/N version 4) assessment will be administered by the CCTS exercise physiologist ([name]) during set-up for the DXA scan. This is a 5 minute survey that can easily be administered by the technician while the DXA scan is calibrated. This survey will be completed at baseline, midpoint, and endpoint by the same DXA technician prior to the DXA scan.

9.1.3 Dual-Energy X-ray Absorptiometry (DXA)

Total body DXA scans will be performed using a GE Healthcare Lunar iDXA (Lunar Inc., Madison, WI) bone densitometer. The subjects will be instructed to remove all objects such as jewelry or eyeglasses and will wear only a standard hospital gown or t-shirt and shorts containing no metal during the scanning procedure. All scans will be analyzed by a trained investigator using the GE Healthcare Lunar Encore software version 14.10. Total body and regional DXA bone mineral content (g), DXA bone mineral density (g/cm²), DXA fat-free mass (FFM; kg), DXA fat mass (kg), and DXA mineral-free lean mass (kg), and DXA percent fat (DXA %Fat) will be assessed.

9.2 Blood and Saliva Collection for Plasma Nitrate, Nitrite and 25(OH)D, and Saliva Nitrate and Nitrite Measures

Following the DXA scan, participants will remain in the CCTS for blood and saliva collection by trained CCTS phlebotomists (will occur between 25-30 minutes post supplement administration on all testing days). Venous blood samples (~8mL) will be drawn into lithium-heparin tubes (low nitrate/nitrite). Within 3 minutes of collection, samples are centrifuged at 4,000rpm at 4C for 10 minutes. Plasma will be extracted and immediately frozen at -80C for later analysis of plasma nitrate (NO₃⁻) and nitrite (NO₂⁻) at the end of the study period.

Saliva will be collected by study personnel at 30 minutes post supplement administration. Subject will generate saliva and place in a collection tube. Sample saliva (200 μ L) will be taken from the tube and placed in a separate tube. Sample will be vortexed and centrifuged for 10 minutes. Supernatant will be removed and stored at -80C for shipment and later analysis.

9.3 Assessment of Muscle Strength and Endurance

Upper body muscle strength and endurance will be assessed by the CCTS exercise physiologist using a handgrip dynamometer (29) and overseen by Drs. [name] and [name] at all three study time points. Strength and endurance measures will be collected after the blood draw and will not occur more than one hour following testing day beet root administration or at the time of arrival in the unit for the observational cohort. Strength will be determined for both the dominant and non-dominant hands using peak force determination from 3 trials. Determining the absolute and relative decline in contractile force at 30, 60, and 90 sec of sustained contraction will assess muscular endurance. Lower body strength and endurance will be assessed by completing a one-legged MVC using a Biodex isokinetic machine.

9.3.1 Isokinetic Strength and Endurance Testing

Before the start of maximal isokinetic force (strength) testing, the participant will be instructed on proper lifting and breathing techniques. Isokinetic strength at 60⁰ per second will be determined in the subject's dominant leg in a seated position with knee and hip angulation of 60⁰ and 120⁰ degrees respectively. During this time, subjects will be provided with strong verbal encouragement and provided with visual feedback of torque on a computer monitor to help with achievement of their best effort. To minimize the use of muscles other than the knee extensors, participants will be stabilized with two shoulder straps, and a waist strap. Strength will be recorded as the highest force generated during one set of 3-4 trials starting at a knee angle of 90⁰. Before recording the maximal effort, 3 trials will be given at a moderate intensity to provide for further muscle warm-up. A two minute rest period will be given between each strength trial. Following isokinetic strength testing of the dominant leg, endurance and fatigability will be assessed by having the participant complete 25 reps at an angular velocity of 240⁰ per second followed by another strength trial. The fall in peak torque and power will be used to calculate fatigability and endurance capacity of the muscle.

9.3.2 Handgrip Strength

Subjects will use a handgrip dynamometer for the assessment of handgrip strength in their dominant and non-dominant arm. The participant will be in a standing position, arms at their side, not touching their body, and elbow bent slightly. The participant will squeeze the dynamometer with as much force as possible, being careful to squeeze only once for each measurement. Three trials will be made with a pause of about 10-20 seconds between each trial to avoid the effects of muscle fatigue. Each trial will be recorded to the nearest pound or kilogram. If the difference in scores is within 6.6 lbs. or 3 kgs., the test is complete. If the difference between any two measures is more than 6.6 lbs. or 3 kgs., then the test will be repeated once more after a rest period.

9.4 Diet and nutrition status monitoring

Nutrition intake data will be collected randomly within a two week period at baseline and midpoint and will not be scheduled on CCTS testing days. All nutrition data collection and management procedures will be overseen by [name] in collaboration with the MCC registered dietitian.

Twenty four hour dietary recalls will be collected in-person twice at baseline and midpoint (4 total 24-hr recalls per subject) by a nutrition graduate student trained in dietary assessment. During clinical status checks/chemo visits at the MCC, participants will be asked to report their food and beverage intake (enteral and/or by mouth) over the previous 24-hours. The Nutrition Data System for Research software (NDSR version 2012, Minneapolis, MN) will be used to organize and assess all dietary data collected. NDSR uses the multiple-pass method to help improve the validity of dietary data. This method is a standardized recall strategy that refers to the number of times a participant's food intake is reviewed during the interview in - an effort to improve recall accuracy (10, 11). Enteral feeding regimens during the 7 week IMRT period will also be monitored closely with clinical progress notes and communication with the MCC registered dietitian to document feeding interruptions, change in formula type, volume, and tolerance. Subjects will also provide a daily beet root juice intake diary (Appendices C and D) and side effect profile. A comprehensive summary of nutrient analysis reports will be generated for all participants.

9.5 Other Study Measures Occurring Weekly

9.5.1 Mucositis

Severity of mucositis will also be evaluated and documented by the treating radiation oncologist, who will be blinded to the group assignment, according to the CTCAE v. 4.0 (Appendix B).

10. STUDY CALENDAR

10.1 Baseline Evaluations/Assessments

Baseline evaluations must be done \leq two weeks prior to protocol therapy, except for radiologic assessments, which must be performed < 21 days prior to the initiation of therapy. The “on-study” tumor assessment can be from archival material.

10.2 Calendar for Beetroot Supplementation Cohort

Timepoints	Baseline	Weekly during Concurrent Radiation and Cisplatin	Midpoint (After IMRT)	Endpoint (4-6 weeks following Midpoint testing)	Off-treatment	Off study
Studies:						
H&P ¹ VS	X	X	X	X	X	X
TOX	X	X	X	X		
Pregnancy Testing	X					
Muscle Strength and Endurance Testing	X		X	X		
Body Composition (DXA)	X		X	X		
Plasma/Salivary Nitrate/Nitrite	X		X	X		
QOL and Mucositis	X		X	X		
Diet	X		X			
Ct SCAN (body comp)	X		X	X		
Routine Cancer Imaging ²	X			X		X
Treatments:						
Beet Root (daily) ³	X	X	X	X		

1) Abbreviations: H&P=History and Physical examination; PS=ECOG performance status; VS=vital signs (blood pressure, temperature, pulse and respiratory rates, weight and height); TOX=toxicity assessment

2) Routine cancer imaging will be standard of care CT or MRI scans to document disease and response to therapy. These will be required pre-treatment, post-chemoradiation and at 1- and 2-year follow-up (+/- 6 weeks), as per standard of care.

3)Beet root will be self-administered each day (M-F in afternoon)

4)Toxicity will be followed for all patients until (endpoint) testing. Any beetroot related toxicity $>$ grade 2 will be followed until resolution to grade 1 or less.

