- CRNs serving as study personnel may offer observation or administration assistance if patient requests this and may document supplement compliance.
- Patients will be instructed to make up any missed doses by taking up to 1 additional dose per day on the weekend days. Patients will receive 5 doses per week (for M-F) and will be instructed to never exceed 1 dose per day.

4-6 weeks post-IMRT (discharge period):

- After completion of IMRT the participant will be instructed to continue daily (M-F) self-administration (PO or PEG) until completion of endpoint measures.
- For patients requiring supplement administration assistance at discharge, a family member or caregiver will be identified and taught to provide assistance.
- On the day of discharge and during scheduled follow-up visits, the CRA will distribute the pre-measured supplement packets needed for daily administration.
- Participants will continue to follow the supplement mixing protocol and be reminded to consume their assigned supplement within 30-minutes of mixing.
- Supplement compliance will continue to be encouraged by weekly phone calls by study personnel and compliance logs/supplement counts will occur at least twice per month.

Supplementation on Testing Days

On testing days, The BEETELITE™ solution (beet root) will be administered on-campus 20-45 minutes before subjects undergo the baseline, midpoint (following IMRT), and endpoint (4-6 weeks following midpoint) strength/endurance measures. Prior to testing, subjects will not have to refrain from standard oral care, using antibacterial mouth wash, or chewing gum 48 hours before testing sessions because the BEETELITE™ product does not rely on salivation/oral bacteria to convert dietary nitrate to nitrite (23). Previous studies have administered up to 500mL of beet root per day with nitrate concentrations of 5.5 mMol (24), 6.2mMol (7, 25), 5.2mMol (26), and 5.1mMol (27). Plasma nitrite (NO_2^-) levels in these aforementioned studies also increased following dietary nitrate supplementation.

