5.4 Duration of Follow Up

The response to treatment will be made by repeating clinical and radiological studies as per standard of care (at 6-12 weeks) and repeated during follow up as per NCCN guidelines. Patients will be followed until resolution of all grade 2 or greater toxicities.

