11. MEASUREMENT OF EFFECT

11.1 Toxicity

For the purposes of this study, patients receiving beetroot supplement will be re-evaluated for toxicity as listed above and weekly during radiation as per institutional standard. All subjects receiving beetroot supplement will be evaluated for toxicity from the time of their first treatment with beet root to the end of study. Subjects will also be required to record each dose of beet root juice, including date and time, and subjective side effects (i.e. nausea, diarrhea, allergic reactions) noted after each dose. Subjects receiving only muscle strength testing will not be followed for toxicity as they receive standard of care and supportive medications as per routine. These subjects are not considered to be part of the interventional study but certainly serve as a baseline observational cohort.

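### For patients who take beetroot to endpoint, the 10.2 calendar schedules no toxicity assessment after the planned last dose, which is inconsistent with 5.2, 5.4 and 11.1 and leaves the 30-day window in 7.3.1 without a scheduled check

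*Combined protocol and SAP*

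**What the plan says.** Section 10.2 (beetroot calendar) marks the toxicity row at baseline, weekly during treatment, midpoint and endpoint. The row is blank under Off-treatment and Off study, although history, physical examination and vital signs are marked in both. Footnote 4 sets the general stop: "Toxicity will be followed for all patients until (endpoint) testing". Its second sentence makes an exception for beetroot-related toxicity above grade 2, which "will be followed until resolution to grade 1 or less".

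Section 5.1.3 tells patients after radiation to "continue daily (M-F) self-administration (PO or PEG) until completion of endpoint measures". It also gives a dose 20-45 minutes before strength testing on each testing day, including the endpoint day.

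Three other rules bear on how long toxicity is followed:

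- Section 11.1: beetroot subjects are "evaluated for toxicity from the time of their first treatment with beet root to the end of study".
- Section 5.4, repeated in 5.2: "Patients will be followed until resolution of all grade 2 or greater toxicities".
- Section 7.3.1: serious adverse events are reportable if they occur after the first dose, during treatment, or "within 30 days of the last dose of treatment on the local institutional SAE form".

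Section 13.4.1 includes all beetroot subjects in the safety analysis and promises incidence tables and a listing that gives the duration of each event.

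**The concern.** Toxicity of beetroot given with radiation or chemoradiation is a secondary objective in section 1.2. The calendar is the page that study staff work from. If they follow it literally, planned toxicity assessment ends on the day supplementation ends, and most events still open that day are no longer followed. Staff who follow 5.4 or 11.1 would continue. The trial could then collect events over different windows for different patients, and the durations listed under 13.4.1 would mix resolved events with events cut off at endpoint.

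The second group dropped by footnote 4, grade 3-4 events not attributed to beetroot, may not be rare. Section 5.1.1.3 expects grade 3-4 mucositis and/or dysphagia in about two thirds of patients. The documents do not say how many such events would still be open at endpoint, 4-6 weeks after midpoint testing.

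**Working it through.** The plan gives no figure to reproduce. The check sets the rules side by side on one time axis.

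**Step 1: the patient who stays on supplement.** Let day 0 be the day of endpoint testing.

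- Planned last dose (5.1.3): day 0. The calendar agrees, since its beetroot row has its last mark at endpoint.
- Last toxicity mark (10.2): day 0.
- Serious-event window (7.3.1): through day 30.
- Toxicity assessments dated by the calendar in days 1 to 30: none. The Off-treatment and Off study columns have no toxicity mark and no stated timing, so it cannot be determined whether their physical examinations fall within the 30 days.

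**Step 2: the patient who stops early but stays on study.** Suppose the last dose is at midpoint. Endpoint is 4-6 weeks later, and 4 × 7 = 28 and 6 × 7 = 42, so the endpoint toxicity assessment falls 28 to 42 days after the last dose. That covers nearly all or all of the 30 days. The gap in Step 1 therefore concerns patients who continue to endpoint, not every beetroot patient.

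**Step 3: when follow-up ends.**

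| Section | Kind of rule | Where it ends |
|---|---|---|
| 10.2, toxicity row and footnote 4 | Assessment schedule and general stop | Endpoint testing |
| 10.2, footnote 4, second sentence | Exception, beetroot-related above grade 2 | Grade 1 or less |
| 11.1 | Toxicity evaluation, all beetroot subjects | End of study |
| 5.2 and 5.4 | Follow-up of toxicity, any attribution | All grade 2 or greater resolved |
| 7.3.1 | Reporting duty, serious events | 30 days after last dose |

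End of study is not defined in 11.1. The calendar has an Off study column after endpoint, with routine imaging marked there, and its footnote 2 calls for imaging at 1 and 2 years. On that reading 11.1 runs past endpoint and cannot be reconciled with the general stop in footnote 4. If end of study instead meant endpoint testing, 11.1 would agree with footnote 4, but the conflict with 5.2 and 5.4 would remain.

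**Step 4: events still open at endpoint.**

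| Event open on day 0 | Under 5.2 and 5.4 | Under 10.2, footnote 4 |
|---|---|---|
| Grade 2, related to beetroot | Followed | Not followed |
| Grade 2, not attributed to beetroot | Followed | Not followed |
| Grade 3-4, related to beetroot | Followed | Followed |
| Grade 3-4, not attributed to beetroot | Followed | Not followed |

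The rules agree in one of the four cells. In the other three, the duration listed under 13.4.1 depends on which section the staff used.

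**The case against.** The strongest reply is that these rules do different jobs. An assessment schedule, a reporting window and a resolution rule often end at different times. This stands for 7.3.1. A reader might infer that it contradicts footnote 4, but it is a duty triggered by an event and can be met without a scheduled visit. Section 7.5 also gives every adverse event, including those reported through expedited processes, a route into the study data. What remains is that the calendar schedules no check of the 30-day window. The reply does not cover footnote 4 against 5.2 and 5.4, which are all rules on how long toxicity is followed.

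A reader might also infer that the trial has no toxicity assessment at all after dosing. The documents do not support that. Section 11.1, sections 5.2 and 5.4, the second sentence of footnote 4 and the later physical examinations all provide some follow-up, and patients who stop early have later toxicity visits. For the same reason the gap cannot be said to affect all 25 beetroot patients.

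A third tempting inference is that the safety tables are materially biased toward fewer events. Section 7.1 lists cramping or diarrhea, coloration and allergic reactions, and names no delayed effect after stopping. No rate of late or unresolved events is given. Truncated durations follow from the text as a possibility, but a bias of known size does not.

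**Conclusion.** The point holds as an internal inconsistency with a practical consequence. For patients who continue beetroot to endpoint, the calendar schedules no toxicity assessment after the planned last dose, and footnote 4 drops three of the four kinds of open event in Step 4 that 5.2 and 5.4 retain. Event durations in the 13.4.1 listing can be truncated as a result, and the time over which events are collected can vary with the section followed. The number of patients and events affected, and the size of any effect on the safety tables, cannot be computed from the documents.

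This rests on two readings: that the last dose is taken on the endpoint testing day as 5.1.3 plans, and, for the conflict with 11.1 only, that end of study lies after endpoint testing. The sponsor should correct it, because staff following the calendar would stop collecting events that other sections of the same protocol require.

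**What to change.** - State one end of adverse event collection and use it in 5.2, 5.4, 10.2 (toxicity row and footnote 4) and 11.1. It should cover the 30 days after the last dose that 7.3.1 already sets for serious events. Define end of study in 11.1 or replace the term.
- Reconcile footnote 4 with 5.2 and 5.4 so that one grade threshold and one attribution rule decide which open events are followed. The choice is the sponsor's.
- Add a toxicity mark to the Off-treatment column in 10.2, where a physical examination is already scheduled, and give that column a stated timing so that it checks the 30-day window.

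The weekly compliance calls in 5.1.3 cannot serve this purpose as they stand, because they run between midpoint and endpoint; a call 30 days after the last dose would be a new contact.

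The cost is a wording amendment, one added toxicity assessment at a contact already in the calendar, and a few more recorded events. Because that contact is undated, fixing its timing may mean moving it for some patients.
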